**Table 1 Objectives and Corresponding Endpoints (cont.)**

Safety Objective(s)	Corresponding Endpoints

 
To evaluate the safety of gantenerumab compared with placebo
 
	
 
Nature, frequency, severity, and timing of adverse events and serious adverse events
 
Physical examinations (including neurological systems), vital signs, blood tests, ECGs, and C-SSRS
 
Nature, frequency, severity, and timing of MRI findings: ARIA-E and ARIA-H
 
Nature, frequency, severity, and timing of injection-site reactions
 
Presence of ADAs during the study relative to the presence of ADAs at baseline (in active drug group only)
 

Pharmacodynamic Biomarker Objective	Corresponding Endpoints

 
To evaluate the effect of gantenerumab compared with placebo
 
	
 
Change from baseline to Week 116 in brain amyloid load, as measured by amyloid PET scan in a subset of participants
 
Change from baseline to Week 116 in brain tau load, as measured by tau PET scan in a subset of participants
 
Change from baseline to Week 116 in cerebrospinal fluid markers of disease in a subset of participants, including, but not limited to total tau, and phosphorylated tau
 

Exploratory Biomarker Objective	Corresponding Endpoints

 
To evaluate the effect of gantenerumab compared with placebo
 
	
 
Change over time in plasma and other CSF biomarkers
 
Change from baseline to Week 116 in functional brain connectivity, as measured by resting-state functional MRI (where available)
 
Change from baseline to Week 116 in integrity of white matter, as measured by DTI-MRI (where available)
 
Change in MRI-derived measurements over time, such as volumetric changes in whole brain, ventricles, hippocampus, or other structures, in all participants
 

AD = Alzheimer's disease; ADA = anti-drug antibody; ADAS-Cog11 = Alzheimer Disease Assessment Scale-Cognition, Subscale 11; ADAS-Cog13 = Alzheimer Disease Assessment Scale-Cognition, Subscale 13; ADCS-ADL = Alzheimer Disease Cooperative Study Group-Activities of Daily Living; ARIA-E = amyloid-related imaging abnormalities-edema/effusion; ARIA-H = amyloid-related imaging abnormalities-hemosiderin deposition; CDR = Clinical Dementia Rating; CDR-GS = Clinical Dementia Rating global score; CDR-SB = Clinical Dementia Rating-Sum of Boxes; CSF = cerebrospinal fluid; C-SSRS = Columbia-Suicide Severity Rating Scale; DTI = diffusion tensor imaging; EQ-5D = EuroQol-Five Dimensions; FAQ = Functional Activities Questionnaire; MMSE = Mini-Mental State Examination; MRI = magnetic resonance imaging; NPI-Q = Neuropsychiatric Inventory-Questionnaire; PET = positron emission tomography; QoL-AD = Quality of Life-Alzheimer's Disease; RUD-Lite = Resource Utilization in Dementia-Lite; SC = subcutaneous; ZCI-AD = Zarit Caregiver Interview-Alzheimer's Disease.

[figure not shown]
## 1.2 STUDY DESIGN

GRADUATE I and GRADUATE II are two identical Phase III, multicenter, randomized, double-blind, placebo-controlled, parallel-group studies designed to evaluate the efficacy and safety of gantenerumab in participants with early (prodromal to mild) AD.

The planned number of participants for the global enrollment phase for each study is approximately 1016 participants randomized in a 1:1 ratio to receive active drug or placebo (508 participants randomized to active drug and 508 randomized to placebo; see Section 3). To maintain a balanced number of participants enrolled in each treatment arm and to ensure that the arms are comparable, randomization will be stratified by stage of the disease (prodromal AD vs. mild AD), apolipoprotein  $\epsilon$ 4 (APOE) allele status (presence vs. absence of the  $\epsilon$ 4 allele), use of AD medication (presence vs. absence), geographic region (Western Europe and Australia vs. Rest of the World vs. North America), and participation in the longitudinal amyloid and tau PET substudies. Approximately 175 centers in approximately 15 countries worldwide will participate in these studies.

Due to the global impact of the coronavirus disease (COVID-19) pandemic and the resulting disruption in study drug administration, the duration of the double-blind treatment period was extended by 12 weeks, with Protocol Amendment 4. The optional scenario of a further extension of 12 weeks – resulting in a final efficacy and safety visit at Week 128 – was not implemented. An overview of the study design is provided in [Figure 1](#).

**Figure 1 Overall Study Design**

Each study consists of three distinct periods:

**Screening** (including an optional prescreening): The screening period may last up to 12 weeks for each eligible participant.

**Double-blind treatment period:** After screening, participants who meet all eligibility criteria will be randomly assigned to one of two arms (active drug or placebo) in a 1:1 ratio. Following baseline assessments, each participant will receive a minimum of 9 subcutaneous (SC) administrations every 4 weeks (Q4W) of study drug (uptitration period), followed by up to 40 administrations every 2 weeks (Q2W) of study drug at target dose in the double-blind treatment period. The last dose of study drug will be administered at Week 114. At the end of the double-blind treatment period, 2 weeks after the last dose, all participants will undergo the final efficacy and safety study visit. Participants who have already completed the double-blind treatment period prior to implementation of Protocol Version 4 will have received up to 34 SC Q2W administrations of study drug during the double-blind treatment period. The last dose will have been administered at Week 102, and their final efficacy and safety visit will be at Week 104.

The Sponsor will emphasize to Investigators the importance of collecting data for the primary endpoint through Week 116, even if participants withdraw from treatment but do not withdraw from the study.

**Post-double-blind treatment period:** After the final efficacy and safety study visit for the double-blind treatment period, all participants will be asked to come back for the long-term follow-up visits or to continue in the open-label extension (OLE). Participants will either directly enter the separate WN42171 (hereafter referred to as “POSTGRADUATE”) OLE study or enter a parent study OLE period. If entering the parent study OLE period, they will be required to complete the uptitration period (a minimum 36 weeks) following which they will then be able to roll over to the

POSTGRADUATE OLE study. This second option is for participants at sites where POSTGRADUATE is not yet approved when they have reached the end of the double-blind treatment period.

### **China Enrollment Plan**

Based on historical data, participant recruitment is expected to take longer in China and therefore, a specific China enrollment plan has been established. Thus, if at least 1 participant is enrolled at sites in mainland China, Hong Kong, and Taiwan that are recognized by the National Medical Products Administration (NMPA) during the global enrollment phase, additional participants may be enrolled in a China extension to ensure a total enrollment that is sufficient to support registration in China. Only participants enrolled at NMPA-recognized sites, during the global enrollment phase, will be included in the primary analysis. All participants enrolled at NMPA-recognized sites, either during the global enrollment phase or the China extension phases, will be included in a China-specific analysis.

The China-specific analysis will be described in a separate SAP and therefore is not covered in this document.

#### **1.2.1 Treatment Assignment and Blinding**

Randomization will be performed centrally using an interactive voice or Web-based response system (IxRS). After screening, participants who meet all eligibility criteria will be randomly assigned to one of two treatment groups (active drug or placebo). The ratio will be 1:1; one active to one placebo. The randomization method will be stratified block-randomization. Randomization to treatment allocation will be stratified by geographic region (Western Europe and Australia vs. Rest of the World vs. North America), participant APOE  $\epsilon$ 4 status (carrier vs. non-carrier), participant stage of disease (prodromal vs. mild AD), use of AD medication (presence vs. absence), and participation in the longitudinal amyloid and tau PET substudies. Except in circumstances in which a Health Authority, Ethics Committee, or Institutional Review Board requires it, a participant will not be told of his or her APOE  $\epsilon$ 4 status. Individual participant APOE  $\epsilon$ 4 genotype results will be blinded to participants, Investigators, and the Sponsor. APOE  $\epsilon$ 4 status information will be supplied directly to the IxRS vendor by the central testing laboratory so that the information can be incorporated at the time of randomization. For participants for whom APOE  $\epsilon$ 4 status is already known, the results will be blinded to the Sponsor and, as much as possible, to the site and central MRI reader.

The study is to be conducted in a double-blind manner to minimize potential bias from Investigators and participants. The Sponsor will be blinded to study treatment. In the OLE phase, the Sponsor, participants, and site staff will remain blinded to previous treatment allocation.

The randomization method implemented in the China extension cohort will be the same as that implemented in the global population.

### **1.2.2 Independent Review Facility**

MRI scans will be reviewed by a central MRI core laboratory, which will perform the diagnostic reads and assessment of MRI outcome measures.

Central facilities will be used for PET assessments (see Independent Review Charter [IRC]).

### **1.2.3 Data Monitoring Committee**

The iDMC will evaluate participant safety and efficacy on a regular basis. In addition to the data defined in the iDMC Charter (e.g., the incidence and nature of adverse events [AE], serious adverse events [SAE], adverse events of special interest [AESI], amyloid-related imaging abnormalities-edema/effusion [ARIA-E], amyloid-related imaging abnormalities-hemosiderin deposition [ARIA-H], and injection-site reactions [ISR]), the iDMC will review all necessary cumulative data at regular intervals during the study, including efficacy when needed. It is anticipated that these assessments will occur approximately every 3 months. At the time of each review, the iDMC will make appropriate recommendations (e.g., the study should continue as planned, enrollment in a specific arm should be discontinued, the treatment regimen should be modified, the protocol should be amended, enrollment should be held pending further safety evaluations). The iDMC will also evaluate planned or unplanned interim analyses for efficacy or futility.

## **2. STATISTICAL HYPOTHESES**

The primary efficacy analysis will compare the active drug arm to the placebo arm at Week 116 with a two-sided test corresponding to the following null hypothesis,  $H_0$ , and alternative hypothesis,  $H_1$ :

$$H_0: \mu_{\text{active}} = \mu_{\text{placebo}}$$

$$H_1: \mu_{\text{active}} \neq \mu_{\text{placebo}}$$

Where  $\mu_{\text{active}}$  and  $\mu_{\text{placebo}}$  are the mean change from baseline to Week 116 in the CDR-SB score for each arm.

## **3. SAMPLE SIZE DETERMINATION**

Determination of sample size is based on participants enrolled in the global enrollment phase. In each study, approximately 1016 participants will be enrolled and randomized in 1:1 ratio to each treatment arm (active drug or placebo) during the global enrollment phase. The original planned sample size was of 760 participants, but it was increased to 1016 participants based on considerations from external studies (in protocol version 3).

Additional participants may be randomized during the China extension if at least 1 participant is enrolled at sites in mainland China, Hong Kong, or Taiwan that are recognized by the NMPA during the global enrollment phase.

The estimated sample size required to demonstrate efficacy with regard to Clinical Dementia Rating-Sum of Boxes (CDR-SB) is based on the following assumptions:

- the mean change in the CDR-SB from baseline to Week 104 is 2.5 points in the placebo arm
- a common standard deviation across treatment arms for change of approximately 2.97 from baseline to Week 104 in the CDR-SB
- active drug has a true effect of a 30% relative reduction in deterioration of CDR-SB

Based on these assumptions, and using a student's T-test with equal variance, a sample size was calculated for 90% power to detect a true treatment effect of 30% relative reduction in deterioration of CDR-SB at a two-sided  $\alpha$  of 0.05.

Uncertainties on parameters affecting the power (e.g., dropout rate, study drug discontinuation rate, standard deviation, and placebo decline) were assumed to be equivalent to a drop in sample size of up to around 35% and were corrected for accordingly. This calculation leads to a total of 1016 participants in the study.

At the date of writing Protocol Version 4, it was expected that participants would miss an average of 8 weeks of study drug administration over the course of the original two-year study due to the COVID-19 pandemic. This had the potential to decrease the power of the study from ~90% to ~80%. To mitigate the impact of missed administrations, the double-blind treatment period has been extended by 12 weeks. Under current assumptions, this brings the study power back to the originally planned ~90%.

#### **4. ANALYSIS SETS**

The following analysis sets are defined:

**Table 2 Analysis Sets**

Analysis set	Definition	Scope
All enrolled participants	All participants randomized during the global enrollment phase whether or not the participant received the assigned treatment. Analysis using this analysis set will be performed by randomized treatment.	Participant disposition report will be based on this analysis set
Intent-to-treat (ITT)	All participants randomized during the global enrollment phase, who received at least one dose of study drug. Analysis using this analysis set will be performed by randomized treatment.	All efficacy analyses, including the primary estimand, will be based on this analysis set.
CSF modified intent-to-treat (CSF-mITT)	All participants in the ITT analysis set who had at least one valid quantitative cerebrospinal fluid (CSF) measurement Analysis using this analysis set will be performed by randomized treatment.	All analyses of CSF biomarkers will be based on this analysis set
CSF-longitudinal	All participants in the CSF-mITT who had at least one valid quantitative Week 116 CSF measurement of phosphorylated tau (pTau-181), tTau, Neurogranin or NFL.	Summary of treatment group comparability will also be repeated on this analysis set.
Plasma-longitudinal	All participants in the ITT analysis set who had at least one valid quantitative post-baseline plasma measurement of Amyloid beta (1-42) (Aβ 42 ) or phosphorylated tau (pTau-181)	Summary of treatment group comparability will also be repeated on this analysis set.
MRI modified intent-to-treat (MRI-mITT)	All participants in the ITT analysis set who had at least one valid volumetric MRI quantitative measurement. Analysis using this analysis set will be performed by randomized treatment.	All analyses of volumetric MRI parameters will be based on this analysis set.
MRI-longitudinal	All participants in the MRI-mITT with at least one valid post-baseline volumetric MRI quantitative measurement.	Summary of treatment group comparability will also be repeated on this analysis set.
Tau PET modified intent-to-treat (Tau-PET-mITT)	All participants in the ITT analysis set who participated in the Tau PET sub-study and who had at least one Tau PET scan with a valid quantitative measurement and who did not withdraw from the Tau PET substudy before randomization Analysis using this analysis set will be performed by randomized treatment.	All analyses of Tau PET parameters will be based on this analysis set.
Tau-PET-longitudinal	All participants in the Tau-PET-mITT with a valid post-baseline quantitative Tau PET measurement.	Summary of treatment group comparability will also be repeated on this analysis set.

**Table 2 Analysis Sets (cont.)**

Analysis set	Definition	Scope
Amyloid PET modified intent-to-treat (Amyloid-PET-mITT)	All participants in the ITT analysis set who participated in the Amyloid PET sub-study and who had at least one Amyloid PET scan with a valid quantitative measurement performed with either florbetaben or flutemetamol and who did not withdraw from the Amyloid PET substudy before randomization.	All analyses of Amyloid PET parameters will be based on this analysis set
Amyloid-PET-longitudinal	Analysis using this analysis set will be performed by randomized treatment. All participants in the Amyloid-PET-mITT with a valid post-baseline quantitative amyloid PET measurement performed with either florbetaben or flutemetamol.	Summary of treatment group comparability will also be repeated on this analysis set.
Safety-evaluable	All participants randomized during the global enrollment phase who received at least one dose of study drug. Any participant randomized to placebo who received at least one dose (any dose) of active drug will be summarized as having received the active drug. Analysis using this analysis set will be performed by treatment actually received.	All safety analyses (with the exception of Safety MRI) will be based on this analysis set.
MRI Safety-evaluable	All participants in the Safety-evaluable analysis set who had at least one post-baseline safety MRI scan. Analysis using this analysis set will be performed by treatment actually received	All analyses of safety MRI will be based on this analysis set.
Amyloid-PET Safety Evaluable	All participants in the Safety-evaluable analysis set who received at least one dose of radioligand Analysis using this analysis set will be performed by treatment actually received	All safety analysis for the amyloid-PET sub-study will be based on this analysis set.
Tau-PET Safety Evaluable	All participants in the Safety-evaluable analysis set who received at least one dose of radioligand. Analysis using this analysis set will be performed by treatment actually received	All safety analysis for the tau-PET sub-study will be based on this analysis set.

## **5. STATISTICAL ANALYSES**

### **5.1 GENERAL CONSIDERATIONS**

The clinical cutoff date for the primary analysis is defined by the date of the last randomized participant plus 116 weeks.

In the following sections, for all continuous variables for which descriptive statistics are indicated, the following statistics will be reported: the number of observations, the mean, median, standard deviation, and minimum and maximum. The 25th and 75th percentiles

(Q1 and Q3) will also be reported for selected tables. Descriptive summaries of discrete data will include frequencies expressed in terms of number and percentage of participants.

For clinical endpoints and biomarkers assessments, the baseline is defined as the assessment taken at the baseline visit (Day 1) up to and including the day of first study drug intake. If no assessment is reported at the baseline visit up to the day of first study drug intake, the earliest assessment reported after Day 1 and up to the day of second dose or Day 35, whichever is earlier, will be used as baseline. If no assessment is reported either at baseline visit or up to Day 35, an assessment reported at screening will be used as baseline. Day 35 is the latest timepoint allowed for Week 4 visit as per protocol.

For all other assessments, the baseline is defined as the last available assessment prior to first study drug intake, unless specified otherwise.

For biomarkers (CFS and plasma), values below the lower limit of quantification (LLOQ) will be set to  $0.5 \times \text{LLOQ}$ , while values above the upper limit of quantification (ULOQ) will be set to ULOQ. A summary table will be provided to summarize the values below LLOQ and above ULOQ for each treatment arm.

The efficacy analyses will be based on the ITT analysis set (see [Table 2](#)) and will compare the active drug arm against the placebo arm with regards to mean change from baseline to Week 116. Two-sided test hypotheses will be defined in the following sections and the type I error level will be 5%. There are two identical Phase III studies, for each respective study the type I error level will be 5%. In order to protect the overall type I error rate (i.e., at each study level) when incorporating the hypothesis testing of multiple endpoints into the analysis, a fixed sequence testing procedure ([Westfall and Krishen 2001](#)) will be used to adjust for multiple comparisons. Testing of each hypothesis will follow a pre-specified order such that an endpoint would only be tested if the preceding one in the hierarchy was significant at 5% alpha level. The endpoint hierarchy, starting with the primary endpoint and including only confirmatory secondary endpoints, is the following:

1. CDR-SB (Clinical Dementia Rating, Sum of Boxes)
2. ADAS-Cog 13 (Alzheimer's Disease Assessment Scale, Cognitive subscale, 13-item)
3. ADCS-ADL (Alzheimer's Disease Cooperative Study, Activities of Daily Living scale) total score
4. FAQ (Functional Activities Questionnaire)

Missing outcome data will be handled using data imputation aligned with the estimand, see Section [5.3.3](#) for a detailed description of the analysis strategy.

When using a statistical model with baseline covariate adjustment, missing baseline covariate data other than the baseline outcome measure will be imputed to the overall median value for continuous covariates, or will be imputed to the most frequent category for categorical variables. In addition, baseline covariates will be derived from information collected into the eCRF, unless otherwise specified.

In statistical models using change from baseline of a given outcome measure as the dependent variable, there will be no imputation of the baseline outcome value, with the consequence that participants missing the baseline outcome measure will not contribute to the analysis.

The impact of the COVID-19 pandemic on the study and its conduct will be monitored and the overall impact will be assessed and described in the Clinical Study Reports.

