4.5.5 Cognitive, Functional, and Health Economics Assessments

The assessments described in this section will be performed as outlined in the schedule of activities (see [Appendix 1](#)) and in the order specified in Section 4.6.

Whenever possible, there should be consistency in the rater and study partner who complete the scales for each participant throughout the duration of the study. Potential raters will receive training and be approved by the rating scale contract research organization (CRO) prior to being allowed to administer any cognitive assessments or rating scales in the study.

Whenever possible, cognitive and functional assessments should be performed at the visit timepoints indicated in the schedule of activities (see [Appendix 1](#)). However, in exceptional circumstances for post-randomization visits, if the caregiver, the primary rater, or even the participant cannot perform these assessments as per the schedule of activities, they may be performed up to 4 weeks out of window.

Given that the primary outcome measure in this trial involves subjective judgment, the adequacy of participant and study partner interviews and ratings will be monitored by an endpoint reliability program administered by the rating scale vendor; this is considered an essential part of good research methodology. For the primary endpoint as well as for some other scales, audio recordings may be used for quality assurance purposes. Prior studies have clearly demonstrated that the failure to adequately monitor such ratings can substantially increase the risks of failed trials (Becker and Greig 2008; Kobak 2010).

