Appendix 1: Schedule of Activities (cont.)

Table 5: Schedule of Activities (OLE Day 1 to Week 22: Dose Escalation with Q2W Administration) (cont.)

tomography; PK = pharmacokinetic; Q2W = every 2 weeks; QoL-AD = Quality of Life–Alzheimer's Disease; RBR = Research Biosample Repository; RUD-Lite = Resource Utilization in Dementia–Lite; SC = subcutaneous; UV = unscheduled visit; Wk = week; ZCI-AD = Zarit Caregiver Interview–Alzheimer's Disease.

B = before study drug administration; P = participant completion; P&SP= participant and study partner completion; SP=study partner.

Notes: The visit window is \pm 3 days for dosing days and +3 days for OLE non-dosing Day 4. Participants should return to initial planned schedule per randomization for subsequent visits.

- ^a OLE Day 1 dosing should take place approximately 2 weeks after final efficacy visit has been completed.
- ^b Visit suitable for home administration of gantenerumab.
- ^c Accurate recording of the date and time of study drug administration and PK sampling is critical. A PK sample will be obtained as soon as is practical (e.g., at an unscheduled visit) once the site becomes aware of the occurrence or worsening of ARIA-E or of the occurrence of ARIA-H meeting discontinuation criteria
- ^d Serum chemistry includes AST, ALT, alkaline phosphatase, total protein, total bilirubin, serum albumin, creatine phosphokinase, sodium, potassium, calcium, BUN, and serum creatinine (and creatinine clearance calculated by the central laboratory). At early termination, hemoglobin A1C, glucose, insulin, total cholesterol, HDL, LDL, triglycerides, C-reactive protein, folic acid, vitamin B-12, T4, free T4, and thyroid-stimulating hormone levels will also be assessed and should ideally be collected at least 4 hours after meals.
- ^e Hematology includes hemoglobin, hematocrit, RBC count (with morphology), WBC counts, platelet, basophil, eosinophil, lymphocyte, monocyte, neutrophil, and WBC–other total counts.
- ^f A complete physical examination includes an evaluation of the head, eyes, ears, nose, and throat, and the cardiovascular, dermatological, musculoskeletal, respiratory, gastrointestinal, genitourinary, and neurological systems.
- ^g Limited, symptom-directed physical examinations; changes from baseline abnormalities should be recorded in participant notes.

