#### Time Windowing

For the primary endpoint (and in general for clinical efficacy endpoints) the following time windows will be used for analyses (see [Table 4](#)), based on study days. Study days are defined based on days on study since the date of the first dose, with the day of the first dose being study day 1.

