**Table 4 Time windows for clinical endpoint assessments**

Visit	Target day	Time window (in study days*)
Baseline	1	Up to Day 35
Week 24	169	72, 266
Week 52	365	267, 448
Week 76	533	449, 630
Week 104	729	631, 770
Week 116	813	771, earliest between 897 or first dose of OLE

In cases where more than one assessment falls within a time window, the assessment with the date closest to the target day is selected whether it's a scheduled, unscheduled or an early termination visit.

With regards to an ICE of withdrawal from study treatment, an assessment will be regarded as having happened after the ICE of withdrawal from study treatment if it is collected >28 days since the last dose.

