**Table 12 Time windows for Volumetric MRI assessments**

Visit	Target study day	Time window
Baseline	1	Up to Day 35
Week 48	337	253, 421
Week 104	729	645, 770
Week 116	813	771, 897

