## **5.8 INTERIM ANALYSES**

Details of interim analysis plans are described in a separate interim analysis SAP (iSAP), providing information about a futility interim analysis based on the primary efficacy endpoint CDR-SB.

Other than the futility analysis, there is no plan for an efficacy interim analysis based on the primary endpoint. The primary analysis of the clinical efficacy endpoints will be performed only once, after completion of the efficacy data collection at the end of the double blind part of the study (as described in this SAP) and it will be the only opportunity to formally reject the primary null hypothesis of the trial.

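### Two upper-end rules for Week 116 data need correcting: the volumetric MRI window has no open-label stop, and the primary cut-off is not reconciled with the Week 116 window

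*SAP*

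**What the plan says.** **Open-label stop.** For clinical endpoints, the Week 116 row of SAP Table 4 reads "771, earliest between 897 or first dose of OLE". SAP 5.6 likewise ends double-blind safety data the day before the first OLE dose. SAP Table 12, "Time windows for Volumetric MRI assessments", gives Days 771 to 897 for Week 116 and does not mention the OLE. The Week 116 rows for amyloid PET (Table 7), tau PET (Table 9), CSF (Table 10) and plasma (Table 11) also end at Day 897 without a stop. The volumetric model in SAP 5.7.9 has no exclusion for open-label scans, and SAP Table 2 analyses the MRI set by randomised arm. On OLE timing, Protocol Appendix 1 (Table 5, footnote a) says "OLE Day 1 dosing should take place approximately 2 weeks after final efficacy visit has been completed". It schedules an MRI before the OLE Week 12 dose, at least 7 days ahead of dosing.

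**Cut-off.** SAP 5.1 says "The clinical cutoff date for the primary analysis is defined by the date of the last randomized participant plus 116 weeks". Table 4 counts days from a different origin, "with the day of the first dose being study day 1", and accepts Week 116 assessments up to Day 897. Protocol 4.5.5 says of cognitive and functional scales that, in exceptional circumstances, "they may be performed up to 4 weeks out of window". SAP 5.8 says the primary analysis "will be performed only once, after completion of the efficacy data collection at the end of the double blind part of the study".

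**The concern.** The SAP recognises that data collected after open-label dosing do not belong in the double-blind comparison, and it guards the clinical and safety analyses accordingly. Volumetric MRI lacks that guard although its schedule places a scan in the gap. A scan from a placebo participant who has since received active drug would then enter the placebo arm of a placebo-controlled comparison.

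The cut-off raises a different problem. Four statements bear on which Week 116 CDR-SB scores count: the cut-off, the analysis window, the late-visit allowance and the timing of the analysis. They do not agree for the last participants enrolled. Which primary-endpoint observations are in should not be left to interpretation at database lock.

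**Working it through.** **The plan's own figures.** Target day = 7 × weeks + 1. Week 104 gives 729 and Week 116 gives 813, as in Table 4. The Week 116 lower bound is the midpoint (729 + 813)/2 = 771, and the upper bound is 813 + 84 = 897.

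**1. Volumetric MRI, Week 104 completer entering this study's OLE**

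- Final double-blind visit and MRI: Day 729, which belongs to Table 12's Week 104 row (645 to 770).
- OLE Day 1: 729 + 14 = Day 743.
- Active doses for a former-placebo participant (Protocol Table 4): OLE Day 1, Week 4 and Week 8, that is Days 743, 771 and 799.
- OLE Week 12 dose: 743 + 84 = Day 827, so the MRI is due by 827 − 7 = Day 820.
- Day 820 lies inside 771 to 897 and is 820 − 813 = 7 days from target.
- Next scheduled OLE MRI: before the Week 24 dose at 743 + 168 = Day 911, so by Day 904, normally after the window. The Day 820 scan is therefore normally the only scheduled one in the Week 116 window.
- With Table 4's stop, this participant's window would end at Day 743, before it opens at Day 771, leaving no Week 116 value. SAP 5.3.3 already treats Week 116 as missing for such participants on the primary endpoint.

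*Week 116 completer entering the OLE.* OLE Day 1 is 813 + 14 = Day 827, and the Week 12 MRI is due by 827 + 84 − 7 = Day 904. It can fall after the window, and the Day 813 scan would be the closest to target.

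*Other biomarkers.* Routine OLE plasma is at OLE Week 24: Day 911 for a Week 104 completer and 827 + 168 = Day 995 for a Week 116 completer, both outside the window. OLE CSF is scheduled only at early termination. PET timing sits in substudy protocols that are not supplied.

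**2. Cut-off**

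- 116 × 7 = 812 days after randomisation, which is Day 813 if the first dose is given on the day of randomisation. With a gap of L days it is Day 813 − L; for example, L = 7 gives Day 806.
- Days from cut-off to window closure, with same-day dosing: 897 − 813 = 84.
- Latest assessment the protocol allows, taking the ±3-day dosing-visit window to apply (assumption) plus 4 weeks: 813 + 3 + 28 = Day 844, or 31 days after the cut-off.
- Participants assessed after the cut-off = 1016 × delay / enrolment duration in days. Enrolment duration is not given; assume uniform accrual over 18 to 36 months (548 to 1096 days).

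| Assumed delay past target | 18 months | 36 months |
|---|---|---|
| Every late enrollee 3 days late | 6 (0.5%) | 3 (0.3%) |
| Every late enrollee 31 days late | 57 (5.7%) | 29 (2.8%) |

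The second row is a ceiling, since the 4-week allowance is meant for exceptional circumstances.

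*Power.* SAP section 3 gives a difference of 0.30 × 2.5 = 0.75 and an SD of 2.97. These need 330 per arm for 90.0% power, and 660/0.65 = 1015.4, which reproduces the stated 1016. Losing 5% of 508 per arm leaves nominal power at 97.5%. Losing 5% of the uninflated 330 per arm lowers it from 90.0% to 88.5%.

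**The case against.** **On the MRI window.** SAP section 1 limits the document to the double-blind period and safety follow-up, and OLE volumetry is a separate exploratory endpoint in the protocol. The OLE Week 12 scan is a pre-uptitration safety scan. Table 12 uses only Weeks 48, 104 and 116 after baseline and leaves out the other double-blind MRIs, so it is not shown that the OLE scan would be read for volume. That last point stands, and the conclusion is conditional on it. The scan could be read: Protocol 4.5.9 includes a 3D T1 sequence in study MRIs. A general scope statement also does not override an explicit day window.

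A reader might infer that all five biomarker analyses are contaminated. The documents do not support that: no routine OLE plasma or CSF sample falls in the window, and PET exposure cannot be shown. The SAP's 56-day PET rules, which concern treatment discontinuation or time since last dose, give partial protection. Nor would every OLE entrant matter. Only former-placebo Week 104 completers in this study's own OLE could carry active-drug exposure into the placebo arm.

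**On the cut-off.** The stated date is the last participant's scheduled Week 116 day if dosing starts at randomisation, and Protocol 4.6.1 and 4.6.2 place randomisation at baseline. SAP 5.8 waits for efficacy data collection to finish. A reader might infer that observed primary-endpoint data will be discarded and imputed. No passage says so. What stands is that nothing says the opposite, and the three SAP rules point in different directions.

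**Conclusion.** Both points hold as gaps at the upper end of the Week 116 rules; no error at the lower end of the window is shown.

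The MRI point is the firmer. Table 12 as written admits a post-open-label scan as a double-blind Week 116 value, conditional on that scan being read volumetrically. The number of former-placebo Week 104 completers who entered this study's OLE is not given, so the bias cannot be sized. It is confined to an exploratory imaging analysis outside the testing hierarchy. CDR-SB and the secondary clinical endpoints are protected by Table 4.

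The cut-off point is an unreconciled conflict, not a demonstrated loss of data. If the cut-off were applied literally, the likely loss is a few participants, with a ceiling of about 3% to 6% under the assumed accrual and little effect on power. Its importance lies in the endpoint concerned, not in the size of the effect.

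**What to change.** 1. Change the Week 116 row of SAP Table 12 to read as Table 4 does: "771, earliest between 897 or first dose of OLE". Add the same first-OLE-dose stop to the Week 116 rows of Tables 7, 9, 10 and 11, keeping their own lower bounds. In those four tables this is for consistency and protects against unscheduled or early-termination samples.
2. In SAP 5.1, define the efficacy cut-off as the date on which the last globally enrolled participant completes Week 116, starts the OLE, or reaches the end of the Week 116 window, whichever comes first. Alternatively, keep the present date and state that in-window Week 116 assessments made after it are included. A cut-off set only at the latest protocol-permitted visit (Day 844) would still precede window closure.

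The cost is SAP wording and a modest delay to the data cut. With same-day dosing, the delay is at most 84 days, reached only if the last participant neither attends Week 116 nor starts the OLE. Week 104 completers in the OLE would have no Week 116 volumetric value, as is already the case for their clinical endpoints.
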